10.1.7. Treatment Visit 9 (Day 57; +/- 2 days)

The following procedures will be completed at Treatment Visit 9:

Prior to dosing with study drug, the following procedures will be performed:

1. Vital signs including BP, pulse rate, RR, and temperature (after at least 5 minutes of rest).
2. AEs and concomitant medications, including corticosteroid dose (if applicable) will be recorded.
3. For three days prior to Treatment Visit 9, three once daily first void urine samples for urine albumin/creatinine and protein/creatinine ratios will be collected and brought for analysis at this visit.
4. Laboratory samples will be collected for:
 - Serum or urine pregnancy test in women of childbearing potential. If the test result is positive then the subject will be discontinued from the study and followed for outcome of the pregnancy
 - Serum PK sample
 - Serum PD sample
 - Serum ADA

Study drug will be administered by IV infusion over 30 minutes.

After dosing with study drug, the following procedures will be performed:

1. Vital signs will be taken including BP, pulse rate, RR, and temperature (after at least 5 minutes of rest) at the following timepoint: 30 minutes.
2. Serum PK samples will be taken at the following timepoint: 30 minutes.
3. Serum PD samples will be taken at the following timepoint: 30 minutes.

CONFIDENTIAL

No use, disclosure or reproduction outside of Omeros without prior written authorization

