8.3. Subject Withdrawal Criteria

8.3.1. Early Discontinuation of Study Drug

Subjects may voluntarily withdraw from the study at any time and for any reason without prejudice to further treatment. A subject must permanently discontinue study drug under any of the following circumstances:

- The subject becomes pregnant. Study drug must be discontinued immediately and the pregnancy reported to the Sponsor.
- The subject wishes to discontinue study drug treatment for any reason.
- The subject experiences a medical emergency that necessitates discontinuing study drug treatment.
- The Investigator, Sponsor, or subject's primary care physician decides to discontinue treatment for medical reasons or due to the subject's noncompliance with the protocol.
- For Cohort 1 subjects, the subject experiences deterioration of renal function during corticosteroid tapering period, as determined by the Investigator.

The reason for termination of study drug before study completion must be recorded in the subject's case report form (CRF). The subject should complete all scheduled study visits provided written consent to do so has not been withdrawn.

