8.3.2. Subject Withdrawal from the Study

A subject must be withdrawn from the study and discontinue study drug under the following circumstances:

- The subject withdraws consent to participate in the study.
- The Investigator or subject's primary care physician decides that the subject should be withdrawn from the study.
- The Sponsor decides that the subject should be withdrawn or the Sponsor discontinues the study for any reason.

The reason for withdrawal must be recorded in the subject's CRF. The subject should complete the evaluations scheduled for the Follow-Up Visit 1, provided written consent to do so has not been withdrawn. Subjects who are withdrawn may be replaced at the discretion of the Sponsor in consultation with the Investigator in order to meet study objectives.

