10.1.5. Treatment Visit 5 (Day 29; +/- 2 days)

The following procedures will be completed at Treatment Visit 5:

Prior to administering the dose of study drug, the following procedures will be performed:

1. Vital signs including BP, pulse rate, RR and temperature (after at least 5 minutes of rest).
2. AEs and concomitant medications, including corticosteroid dose (if applicable) will be recorded.
3. For three days prior to Treatment Visit 5, three once daily first void urine samples for albumin/creatinine and protein/creatinine ratios will be collected and brought for analysis at this visit.
4. Laboratory samples will be collected for:
 - Serum or urine pregnancy test in women of childbearing potential. If the test result is positive then the subject will be discontinued from study drug administration and followed for outcome of the pregnancy.
 - Serum PK sample
 - Serum PD sample
 - Serum ADA sample

Study drug will be administered by IV infusion over 30 minutes.

After dosing with study drug, the following procedures will be performed:

1. Vital signs will be taken including BP, pulse rate, RR, and temperature (after at least 5 minutes of rest) at the following timepoint: 30 minutes.
2. Serum PK samples will be taken at the following timepoint: 30 minutes.
3. Serum PD samples will be taken at the following timepoint: 30 minutes.
4. At Treatment Visit 5, Cohort 1 subjects with stable or improving renal function should begin corticosteroid tapering and continue through the ensuing 4-week period to prednisone ≤ 6 mg (or equivalent dose), at the discretion of the Investigator.

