10.1.12. Cohort 3 Re-Treatment Visit 1 RT1 (+/- 2 days)

Prior to re-treatment visit 1, subject eligibility for re-treatment must be confirmed. OMS721 will be administered to all subjects undergoing re-treatment.

Prior to administering the dose of study drug the following procedures will be performed:

1. Review of AEs and concomitant medications.
2. Vital signs including BP, pulse rate, RR, and temperature (after at least 5 minutes of rest).
3. ECG taken (after at least 5 minutes of rest in the supine position)
4. Laboratory samples will be collected for:
 - Hematology, chemistry, coagulation, cystatin C
 - Urinalysis
 - Urine for inflammatory biomarkers
 - Serum or urine pregnancy test in women of childbearing potential. If the test result is positive then the subject will be excluded from further treatment, but continue follow-up
 - Blood samples for future research
 - Serum PK sample

CONFIDENTIAL

No use, disclosure or reproduction outside of Omeros without prior written authorization

- Serum PD sample
- Serum ADA sample

Study drug will be administered by IV infusion over 30 minutes.

After dosing with study drug, the following procedures will be performed:

1. Vital signs including BP, pulse rate, RR, and temperature (after at least 5 minutes of rest) at the following timepoints: 30 minutes, 1 hour.
2. ECG taken (after at least 5 minutes of rest in the supine position), to be obtained immediately post dose).
3. Serum PK samples at the following timepoints after end of dosing: 5 minutes, 2 hours, and 24 hours (**Day 2**), 72 hours (**Day 4**).
4. Serum PD sample after the end of dosing: 2 hours.
5. The subject may be discharged after arrangements are made for the collection of PK samples on **Days 2 and 4**.

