10.1.15. Early Withdrawal from the Study

All subjects will be encouraged to complete all evaluations. However, subjects who prematurely discontinue the study will have the assessments for Follow-Up Visit 1 (or Re-Treatment Follow-up Visit 1, if applicable) performed, and will be followed for 30 days if there is a serious adverse event (SAE), if possible.

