12.3. Reporting Adverse Events

12.3.1. Adverse Event Reporting

An AE is defined as any untoward medical occurrence in a subject administered a pharmaceutical product and which does not necessarily have to have a causal relationship with this treatment. AEs may be reported by the subject, discovered by the Investigator and Investigator’s staff, or detected through physical examination, laboratory test, or other means.

AEs include:

- Any unfavorable and unintended sign, medical diagnosis, or symptom that occurs between the time the first administration of study drug and the study duration required by the protocol

- Any new undesirable medical experience or an unfavorable and unintended change of an existing condition that occurs between the time the first administration of study drug and the study duration required by the protocol, whether or not considered related to study drug
- Abnormal laboratory findings considered by the Investigator to be clinically significant, i.e., those that are unusual for the population being studied or individual subject

Whenever possible, the Investigator should group signs or symptoms that constitute a single diagnosis into a single event term. For example, cough, rhinitis, and sneezing might be grouped together as *upper respiratory tract infection*.

In cases where the Investigator notices an unanticipated benefit to the subject, study site personnel should enter *unanticipated benefit* with the actual event term (for example, the complete actual term would be *unanticipated benefit-sleeping longer*).

AEs will be collected from the time informed consent is obtained until the last Follow-Up visit. All AEs will be documented in the source records and will be recorded in the CRFs as appropriate. All AEs, whether observed by the Investigator or reported by the subject, and whether or not thought to be related to the study drug, will be recorded on the appropriate CRF. In describing AEs on the CRF, standard, medically accepted terminology will be used.

The description of each AE will identify the date of onset, duration, severity (see Section 12.2.2 for Definitions of Severity), any action taken (including any diagnostic procedures or laboratory tests performed and all treatments which were administered), the outcome of the event, and relationship to the study drug.

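### Protocol 10.1.7 withdraws a subject with a positive Visit 9 pregnancy test from the study; every other instruction for a dosed subject found pregnant during treatment stops study drug only

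*Protocol*

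**What the plan says.** For a positive pregnancy test at Treatment Visit 9 (Day 57), Protocol 10.1.7 says: "If the test result is positive then the subject will be discontinued from the study and followed for outcome of the pregnancy".

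The general rule is in Protocol 8.3.1, where pregnancy is the first listed reason for permanent discontinuation of study drug: "Study drug must be discontinued immediately and the pregnancy reported to the Sponsor". The same section then says of subjects who stop drug early: "The subject should complete all scheduled study visits provided written consent to do so has not been withdrawn".

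Protocol 8.3.2 lists the reasons for withdrawal from the study: withdrawn consent, or a decision by the investigator, the primary care physician or the sponsor. Pregnancy is not among them. For subjects who do withdraw, 8.3.2 says: "The subject should complete the evaluations scheduled for the Follow-Up Visit 1, provided written consent to do so has not been withdrawn". Section 10.1.15 agrees: "subjects who prematurely discontinue the study will have the assessments for Follow-Up Visit 1", with 30 days of follow-up if there is a serious adverse event.

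At Visit 5 (Day 29), four weeks before Visit 9, Protocol 10.1.5 says of a positive test: "then the subject will be discontinued from study drug administration and followed for outcome of the pregnancy". At Re-Treatment Visit 1, 10.1.12 says: "then the subject will be excluded from further treatment, but continue follow-up", and 10.1.13 repeats this for Re-Treatment Visits 5 and 9. The pregnancy reporting section, 12.3.4, also stops study drug only.

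**The concern.** The two wordings lead to different pathways. A subject off drug continues all scheduled visits (8.3.1). A subject off study has the Follow-Up Visit 1 assessments and then leaves, apart from follow-up of existing events (10.1.15, 12.4). Site staff at Visit 9 work from the Visit 9 text, which gives withdrawal as an instruction and leaves no choice.

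The primary objective is safety, and 12.3.1 says: "AEs will be collected from the time informed consent is obtained until the last Follow-Up visit". Withdrawal at Day 57 ends scheduled collection of new adverse events, safety laboratory tests and anti-drug antibody (ADA) samples in a pregnant subject who may have received OMS721.

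There is also an effect on the analysis set. The efficacy population (Protocol 13.2.1.2, SAP 8.3.3) requires at least one post-baseline 24-hour urine protein. In the initial treatment course none is scheduled before Follow-Up Visit 2 (Day 120), so a subject withdrawn at Day 57 cannot qualify through scheduled collections.

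**Working it through.** The plan gives no figure to reproduce. The check compares every instruction on a positive test or a pregnancy, then counts what the Visit 9 wording would cost one subject.

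**1. Comparison of the instructions**

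| Protocol section | Timing | Action |
|---|---|---|
| 10.1.3 | Day 1, before first dose | Excluded from the study (eligibility) |
| 8.3.1 | Any time on drug | Stop drug; complete scheduled visits |
| 10.1.5 | Visit 5, Day 29 | Stop drug; follow pregnancy outcome |
| **10.1.7** | **Visit 9, Day 57** | **Leave the study; follow pregnancy outcome** |
| 10.1.9 | Follow-Up Visit 1, Day 85 | Follow pregnancy outcome |
| 10.1.12, 10.1.13 | Re-treatment | No further treatment; continue follow-up |
| 10.1.14 | Re-treatment follow-up | Follow pregnancy outcome |
| 12.3.4 | Any time | Report; stop drug |

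The Day 1 rule applies before any dose, and the follow-up rules apply after the last dose of a course, so neither explains the Visit 9 wording. Among instructions for a dosed subject still on treatment, only 10.1.7 removes her from the study.

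**2. Loss per case**

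Inputs are the visit days and sampling marks in Protocol 19.2 and SAP 5.1, with 10.1.9 and 10.1.11 for the 24-hour urines. The Follow-Up Visit 1 (FU1) set is subtracted because it is done at withdrawal.

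Cohorts 1 and 2, to Follow-Up Visit 2 (FU2):
- Time: Day 120 − Day 57 = 63 days = 9 weeks.
- Visits after Day 57: T10, T11, T12, FU1, FU2 = 5; 5 − 1 = 4.
- Hematology/chemistry and ADA sets: FU1, FU2 = 2; 2 − 1 = 1.

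Cohort 3, to Follow-Up Visit 9 (FU9):
- Time: Day 722 − Day 57 = 665 days = 95 weeks.
- Visits: 5 + 7 (FU3 to FU9) = 12; 12 − 1 = 11.
- Hematology/chemistry and ADA sets: 2 + 7 = 9; 9 − 1 = 8.
- 24-hour urines: FU2 + 7 (FU3 to FU9) = 8. None is in the FU1 set, so all 8 are lost.

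**3. Effect on the efficacy population**

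Cohort 3 plans about 18 subjects randomized 1:1 (Protocol 7.1, 9.1.2), so about 18 / 2 = 9 per arm. One subject lost is 1/9, about 11% of an arm. Protocol 13.2.1.1 rules out imputation.

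**The case against.** The strongest reply is that this is a dropped word with no practical effect. The governing rule is in 8.3.1, the withdrawal list in 8.3.2 omits pregnancy, and 12.3.4 names study drug, so a site that reads these has the answer. Subject protection does not depend on the wording: drug stops, the pregnancy is reported and its outcome is followed, and 10.1.15 and 12.4 still cover serious and previously reported adverse events. Cases will be rare, because contraception is required and the trigger is a positive test at one visit. All of this stands, and it is why the point is minor. It does not remove the conflict, because 10.1.7 is an operative instruction to sites.

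Other points also have some force:

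- **The count of sections.** Sections 10.1.5 and 12.3.4 do not themselves say that visits continue, and 10.1.12 and 10.1.13 govern re-treatment. For the first course, continued visits rest on 8.3.1 alone. That is correct, but 8.3.1 is the general rule and is explicit.
- **The value of the lost visits.** T10 to T12 mainly involve dosing, vital signs, adverse event and medication review, and PK/PD sampling, with an ECG at T12. They matter less for a subject already off drug. The later visits carry the safety laboratory, ADA and 24-hour urine data.
- **The efficacy population.** Any withdrawal before Day 120 has the same effect, because the cause is the collection schedule combined with the population definition. The Visit 9 wording is one avoidable route to it. The study is descriptive and not powered for comparisons (Protocol 13.1), so one subject changes no formal inference.
- **Which cohorts collect urine at FU2.** Protocol 19.2 marks the FU2 24-hour urine without a cohort limit, while 10.1.9 dispenses supplies to Cohort 3 only. The tally follows 10.1.9, which is the conservative reading. If 19.2 governs, Cohorts 1 and 2 also lose their single post-baseline collection.

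**Conclusion.** The concern holds: 10.1.7 contradicts 8.3.1 and is out of line with the other on-treatment pregnancy instructions. The intended rule is almost certainly to stop drug and stay in the study. The point is minor.

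The figures are a worst case for a single subject who tests positive at Visit 9. They assume she would otherwise have completed every scheduled visit, which 8.3.1 makes an expectation conditional on consent. The documents give no pregnancy incidence, so no expected number of cases can be stated. The efficacy-population consequence is claimed for Cohort 3 only, on the reading of 10.1.9 given above.

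**What to change.** In Protocol 10.1.7, replace the instruction to leave the study with the Visit 5 wording: "then the subject will be discontinued from study drug administration and followed for outcome of the pregnancy". At Visits 5 and 9, add one clause saying that the subject continues scheduled visits per 8.3.1 unless she withdraws consent. The clause restates the existing rule where site staff will read it; the replacement in 10.1.7 alone cures the contradiction.

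Leave the screening, Day 1 pre-dose and post-treatment test instructions unchanged.

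The cost is one phrase and one repeated clause, which can go into the next amendment. The visits are already scheduled, and neither the protocol's statistical section nor the SAP needs to change.

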10.1.8. Treatment Visit 10, 11, 12 (Days 64, 71, 78; +/- 2 days)

The following procedures will be performed at Treatment Visits 10, 11, and 12:

Prior to dosing with study drug, the following procedures will be performed:

1. Vital signs including BP, pulse rate, RR, and temperature (after at least 5 minutes of rest).
2. AEs and concomitant medications, including corticosteroid dose (if applicable) will be recorded.
3. ECG taken (after at least 5 minutes of rest in the supine position) (visit 12 only).
4. Laboratory samples will be collected for:
 - Serum PK sample
 - Serum PD sample

Study drug will be administered by IV infusion over 30 minutes.

After dosing with study drug, the following procedures will be performed:

1. Vital signs will be taken including BP, pulse rate, RR, and temperature (after at least 5 minutes of rest) at the following timepoint: 30 minutes.
2. ECG taken (after at least 5 minutes of rest in the supine position), to be obtained immediately post dose (visit 12 only).
3. Serum PK samples will be taken at the following timepoint: 30 minutes (visit 12 only).
4. Serum PD samples will be taken at the following timepoint: 30 minutes (visit 12 only).
5. At Treatment Visit 12, provide subjects with supplies to collect first void urine samples for urine albumin/creatinine and protein/creatinine ratios on three mornings prior to Follow-Up Visit 1.

10.1.9. Follow-Up Visit 1 (Day 85; +/- 3 days)

One week after the last dose of study drug, the following procedures and assessments will be performed:

1. Vital signs will be taken including BP, pulse rate, RR, and temperature (after at least 5 minutes of rest).
2. AEs and concomitant medications, including corticosteroid dose (if applicable) will be recorded.
3. Laboratory samples will be collected for:
 - Hematology, chemistry, coagulation, cystatin C
 - Urinalysis
 - Urine for inflammatory biomarkers
 - Serum or urine pregnancy test in women of childbearing potential. If the test result is positive then the subject will be followed for outcome of the pregnancy

CONFIDENTIAL

No use, disclosure or reproduction outside of Omeros without prior written authorization

- Serum PK samples
 - Serum PD sample
 - Serum ADA sample
4. For three days prior to Follow-Up Visit 1, three once daily first void urine samples for urine albumin/creatinine ratios will be collected and brought for analysis at this visit.
 5. For Cohort 3 subjects only, subjects will be provided with supplies to collect 24-hour urine samples in the week prior to next Follow-Up Visit. The investigative site will call the subject one week prior to the next follow-up visit to remind the subject to collect the 24-hour urine sample.
 6. At Follow-Up Visit 1, subjects will be provided with supplies to collect first void urine samples for urine albumin/creatinine and protein/creatinine ratios on three mornings prior to Follow-Up Visit 2.

10.1.10. Follow-Up Visit 2 (Day 120; +/- 3 days)

Six weeks after the last dose of study drug the following procedures and assessments will be performed:

1. Vital signs will be taken including BP, pulse rate, RR, and temperature (after at least 5 minutes of rest).
2. AEs and concomitant medications, including corticosteroid dose (if applicable) will be recorded.
3. Laboratory samples will be collected for:
 - Hematology, chemistry, coagulation, cystatin C
 - Serum PK samples
 - Serum PD sample
 - Serum ADA sample
4. For three days prior to Follow-Up Visit 2, three once daily first-void urine sample for urine albumin/creatinine and protein/creatinine ratios will be collected and brought in for analysis at this visit.

Subjects in Cohort 1 and Cohort 2 will complete the study at Follow-up Visit 2 provided they have not rolled into Cohort 3.

Subjects in Cohort 3 will undergo extended follow-up with visits at weeks 26, 39, 52, 65, 78, 91 and 104.

10.1.11. Cohort 3 Extended Follow-Up Visits (Weeks 26, 39, 52, 65, 78, 91, and 104; +/- 2 weeks)

At each extended follow-up visit the following procedures will be performed:

1. AEs and concomitant medications will be recorded.

CONFIDENTIAL

No use, disclosure or reproduction outside of Omeros without prior written authorization

2. Laboratory samples will be collected for:
 - Hematology, chemistry, cystatin C
 - Urinalysis
 - Urinary 24-hour protein
 - Urine for inflammatory biomarkers
 - Serum ADA sample
3. Subjects will be provided with supplies to collect 24-hour urine samples in the week prior to next Follow-Up Visit. The investigative site will call the subject one week prior to the next follow-up visit to remind the subject to collect the 24-hour urine sample. Subjects will not be provided with collection supplies at the last Follow-Up Visit.

Cohort 3 subjects who have 24-hour urine protein > 1000 mg anytime between weeks 18-91 or 24-hour urine protein \geq 50% of baseline during the follow-up period may elect, with the agreement of the Investigator, to receive open-label OMS721 370 mg IV for 12 weeks. Additional 12-week OMS721 treatment courses may be administered as often as subjects have 24-hour urine protein > 1000 mg or 24-hour urine protein \geq 50% of baseline during weeks 18-91. The visit schedule for each series of additional OMS721 treatment is provided below. If a subject receives re-treatment, the subject's re-treatment visit schedule will be followed until the re-treatment follow-up is completed (see below for re-treatment schedule). At that time, the subject's next visit will be at the first regularly scheduled follow-up visit following the initial OMS721 treatment course.

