Subjects in Cohort 1 and Cohort 2 will remain in the study for 6 weeks following their last study drug dose. Subjects in Cohort 3 will remain in the study for 104 weeks following their first blinded study drug dose.

Clinic visits for subjects in Cohort 1 and Cohort 2 will occur at screening, weekly through the treatment period, and 1, 4, and 6 weeks following the last dose of study drug. Cohort 1 and Cohort 2 subjects will be in the study for approximately 22 weeks.

Clinic visits for subjects in Cohort 3 will occur at screening, weekly through the treatment period and 1, 4, and 6 weeks following the 12th blinded study drug dose at Week 12. Cohort 3 subjects who have 24-hour urine protein < 500 mg will enter the follow-up period with visits at weeks 26, 39, 52, 65, 78, 91 and 104. Cohort 3 subjects who have 24-hour urine protein > 1000 mg or 24-hour urine protein $\geq 50\%$ of baseline anytime between weeks 18-91 during the follow-up period may elect, with the agreement of the investigator, to receive open-label OMS721 370 mg IV once weekly for 12 weeks. Additional 12-week OMS721 treatment courses may be administered as often as subjects have 24-hour urine protein > 1000 mg or 24-hour urine protein $\geq 50\%$ of baseline during weeks 18-91. Subjects in Cohort 3 will be in the study approximately 25 months.

In Cohort 3, data analyses will be performed after the 6-week follow-up period of the initial 12 weeks of study drug treatment for both the exclusive Asian and non-exclusive Asian groups.

Clinical and laboratory assessments will be done at each study visit as shown in [Figure 1](#).

Figure 1: Study Design Schematic

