7.2.1. Rationale for Dose Selection

The dose level of OMS721 370 mg IV in this study inhibits the lectin pathway for approximately one week and provides high levels of lectin pathway inhibition for approximately 4 to 5 days. Prior doses of 4 mg/kg were associated with marked improvement in urinary protein measures in subjects with aHUS, IgA nephropathy, MN, and lupus nephritis. This dose was well tolerated. The fixed dose is within the range of doses provided previously in this study.

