8. SELECTION AND WITHDRAWAL OF SUBJECTS

8.1. Subject Inclusion Criteria

Subjects may be included in the study only if they meet all of the following criteria:

1. Competent to provide informed consent.
2. Voluntarily provide informed consent in accordance with regulations and governing institutional review board (IRB) or independent ethics committee (IEC) requirements prior to any procedures or evaluations performed specifically for the sole purpose of the study.
3. Are age ≥ 18 years at Screening Visit 1.
4. Have a diagnosis of one of the following:
 - IgAN diagnosed on kidney biopsy
 - Lupus nephritis diagnosed on kidney biopsy (Cohort 1 only)

CONFIDENTIAL

No use, disclosure or reproduction outside of Omeros without prior written authorization

- Primary MN diagnosed on kidney biopsy (Cohort 1 only)
 - C3 glomerulopathy including dense deposit disease diagnosed on kidney biopsy (Cohort 1 only)
5. Have 24-hour urine protein > 1000 mg/24 hours.
 6. For subjects in Cohort 1, have been on ≥ 10 mg of prednisone or equivalent dose for at least 12 weeks prior to Screening Visit 1.
 7. If on immunosuppressive treatment (e.g., cyclophosphamide, mycophenolate mofetil), have been on a stable dose for at least 2 months prior to Screening Visit 1 with no expected change in the dose for the study duration.
 8. Have an eGFR ≥ 30 mL/min/1.73 m² calculated by the MDRD equation.
 9. Are on physician-directed, stable, optimized treatment with ACEIs and/or ARBs and have a systolic blood pressure of < 150 mmHg and a diastolic blood pressure of < 90 mmHg at rest.
 10. If female, are either a) not of childbearing potential (i.e., surgically sterilized or postmenopausal for > 1 year), b) have a negative pregnancy test and if sexually active must agree to use two medically reliable forms of contraception throughout the study, or c) have a medically sterilized male partner. Acceptable methods of contraception include a reliable intrauterine device, hormonal contraception, or a barrier method.
 11. If male, are either a) not of reproductive potential or b) if sexually active must agree to use a medically reliable form of contraception throughout the study. Acceptable methods of birth control include spermicide in combination with a barrier method, or subject's female partner is willing to use medically acceptable methods of birth control (intrauterine device, hormonal contraception, or a barrier method).

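### A Cohort 3 re-treatment course started at Week 91 leaves about 14 days of new-AE collection and contraception after the last dose, against 6 weeks after the initial course: a cheap, low-priority improvement

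*Protocol*

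**What the plan says.** **When re-treatment may start.** Protocol 10.1.11 opens it to "Cohort 3 subjects who have 24-hour urine protein > 1000 mg anytime between weeks 18-91", or with protein at least half of baseline during follow-up, if the Investigator agrees. It adds: "Additional 12-week OMS721 treatment courses may be administered as often as subjects have 24-hour urine protein > 1000 mg". No section gives a latest date for the first re-treatment dose (RT1).

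**When the study ends.** Protocol 7.1: "Subjects in Cohort 3 will remain in the study for 104 weeks following their first blinded study drug dose". The Week 104 visit has target Day 722 (Protocol 19.2; SAP Table 2).

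**What follows a course.** After the initial course, 7.1 says for the first two cohorts: "Subjects in Cohort 1 and Cohort 2 will remain in the study for 6 weeks following their last study drug dose". Section 10.1.10 sets the same interval for the visit that closes the initial course: "Six weeks after the last dose of study drug the following procedures and assessments will be performed". After a re-treatment course, 10.1.14 and the schedule in 19.3 provide one visit (RTFU), a week after the last dose. The subject then returns to the regular visit schedule.

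**When safety obligations stop.** Section 12.3.1 ends AE collection at the last Follow-Up visit. Criterion 10 in 8.1 says that sexually active women of childbearing potential "must agree to use two medically reliable forms of contraception throughout the study"; criterion 11 ties the obligation for men to the same period. Section 12.4 keeps following AEs already reported, including SAEs that persist at the last visit. Section 10.1.15 adds 30 days only for subjects who leave the study early with an SAE.

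**The concern.** The end of the study is fixed by the first dose, whereas the end of dosing can move. After an early re-treatment course the remaining scheduled visits keep AE collection running for months. After a late one, almost nothing remains between the last dose and Week 104. An AE or pregnancy that begins in the following weeks would fall outside both the collection period and the contraception requirement. Safety and tolerability is the primary endpoint, and the protocol itself observes subjects for six weeks after every initial course, so the difference deserves a check.

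**Working it through.** **Inputs**

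| Input | Value | Source |
|---|---|---|
| Last initial dose | Day 78 | Protocol 10.1.8 |
| Follow-Up Visit 2 | Day 120 | Protocol 10.1.10 |
| Week 91 and Week 104 targets | Days 631 and 722, each ±14 days | Protocol 19.2, SAP Table 2 |
| 104 elapsed weeks after Day 1 | 1 + 104 × 7 = Day 729 | Protocol 7.1 |
| Last re-treatment dose (RT12) | RT1 + 77, ±2 days | Protocol 19.3 (re-treatment Day 78) |
| RTFU | RT1 + 84 | Protocol 19.3 (re-treatment Day 85) |

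**The plan's own figure.** Initial course: 120 − 78 = 42 days, which is the stated six weeks.

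**A course started on Day 631.** RT12 = 631 + 77 = Day 708. RTFU = 631 + 84 = Day 715. Time after the last dose is 722 − 708 = 14 days to the final visit, or 729 − 708 = 21 days if 104 weeks is read as elapsed time.

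**Where the shortfall begins.** The latest RT1 that leaves 42 days is 722 − 42 − 77 = Day 603, the first day of Week 87. With a Day 729 end it is 729 − 42 − 77 = Day 610.

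**Sensitivity to windows and delay** (the documents give no start delay, so every delay here is an assumption)

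| Case | Days from RT12 to end |
|---|---|
| Day 631 start, RT12 two days early, Week 104 visit on Day 736 | 736 − (631 + 75) = 30 |
| Day 631 start, all on target | 14 (21 to Day 729) |
| RT1 seven days after Day 631 (Day 638, RT12 Day 715) | 722 − 715 = 7 (14 to Day 729) |
| Week 91 visit and RT1 both on Day 617, RT12 two days early, Week 104 visit on Day 736 | 736 − (617 + 75) = 44 |

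Six weeks is thus attainable when every window is favourable, but not on target days. The RTFU keeps the interval from falling much below a week.

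**Earlier courses.** A start on the Week 78 target (Day 540) leaves 722 − (540 + 77) = 105 days. In the least favourable case the Week 78 visit is on Day 554, the assumed delay is 14 days, RT12 is two days late and the Week 104 visit is on Day 708. That leaves 708 − (554 + 14 + 79) = 61 days, so courses triggered at Week 78 need no change.

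**Extra time needed to reach 42 days**

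- Day 631 start: 708 + 42 = Day 750, which is 28 days past Day 722.
- Seven-day delay: 715 + 42 = Day 757, 35 days past.
- Extreme case (visit on Day 645, 14-day delay, RT12 two days late): 645 + 14 + 79 + 42 = Day 780, 58 days past, or about 8 weeks.

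**The case against.** The strongest reply is that the design is coherent as written. Twelve weeks of dosing plus a one-week follow-up fills the 13 weeks from Week 91 to Week 104, and 19.3 labels the re-treatment follow-up as one week. No section gives a safety reason for six weeks. In Cohort 3 the six-week visit also decides open-label eligibility and times the planned analyses (Protocol 7.1, SAP 18). Nor is six weeks a floor throughout the protocol: subjects who leave early have only the Follow-Up Visit 1 assessments, plus 30 days if there is an SAE. Section 7.2.1 says the 370 mg dose "inhibits the lectin pathway for approximately one week", so 14 to 21 days is two to three times that. On target days a Day 631 starter is still seen twice after the last dose. RTFU covers AEs, vital signs, safety laboratory tests, ADA and a pregnancy test; Week 104 covers AEs, hematology, chemistry and ADA.

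All of that stands, and it sets the priority. It does not close the gap. Duration of pathway inhibition does not bound the onset of adverse events or ADA, and the protocol itself samples ADA six weeks after the initial course. Following known events does not capture new ones. Some sections on clinical experience and risk-benefit have no visible text, and consent pages are not available. They might hold half-life data or contraception instructions, but that cannot be assumed either way.

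Two stronger readings should be resisted. One is that RTFU might be skipped once Week 104 has passed; 10.1.11 already says "the subject's re-treatment visit schedule will be followed until the re-treatment follow-up is completed". The other is that the most heavily treated subject necessarily has the shortest observation. Six re-treatment courses (6 × 12 = 72 doses) ending on Day 708 are possible only if the subject qualifies and elects treatment every time with almost no delay; seven-day delays still give six courses, ending on Day 715. With an assumed 14-day delay after each scheduled visit, RT1 falls on Days 134, 281, 463 and 645, which gives four courses and 48 doses.

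**Conclusion.** The concern holds as a cheap, low-priority improvement. On target days a Week 91 course leaves 14 days of new-AE collection and contraception after the last dose (21 to Day 729), against 42 after any initial course. Favourable windows raise this to 30 days for a Day 631 start; a delayed start lowers it below 14. Only courses started after Day 603 fall short on target days. The documents give no re-treatment rate, so the number affected cannot be computed, but it is a subset of about 18 randomized Cohort 3 subjects plus rollovers. The analysis is descriptive and no estimate changes.

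A reader might infer that the protocol contradicts itself, or that two to three weeks is unsafe. The documents support neither. The one-week follow-up is a deliberate choice, and nothing visible shows how long observation must be. What they do show is that earlier courses are covered by later scheduled visits and late ones are not, with no reason given for the difference.

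**What to change.** Amend the text that governs the two obligations: the AE collection period in Protocol 12.3.1, and contraception criteria 10 and 11 in 8.1. Each should run *until the last Follow-Up visit or 6 weeks after the last dose of OMS721, whichever is later*. Add a cross-reference in 7.1 and 10.1.14. Collect the AEs at one contact six weeks after the last dose. A telephone call is enough; laboratory tests and ADA are optional.

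Nothing need be said about completing RTFU. Week 104 stays the efficacy timepoint, and no treatment rule changes. The SAP needs no edit, because footnote 1 of Table 2 already selects the value closest to the target day.

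The cost is a protocol amendment with ethics review, matching consent wording, and about 4 more weeks of contact on target days (at most about 8) for the few subjects affected. For them the contraception obligation lasts correspondingly longer.
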